The eligibility of subjects who have consented participation will be assessed based on the inclusion and exclusion criteria. Study subjects must meet all of the study inclusion criteria and none of the study exclusion criteria to be eligible. Assessments for eligibility include average pain intensity (which will be used as Baseline pain intensity), medication usage, medical records and history, and the Investigator's clinical judgment. Subjects with confirmed eligibility will proceed to Baseline assessment, while subjects who do not will be discontinued from the study.

B.6.4. Baseline

Before a subject is randomized, a subject will be requested to fill out standard questionnaires that will assess extent of disability, use of medications, and quality of life. The medical and surgical history of the subject will be collected. At this visit and subsequent visits, the subject will be assessed for adverse events, medication usage and be reminded to not increase pain medications from baseline through the 3-Month Visit.

Pre-operative assessments will follow the standard of care for SCS therapy and be determined by the site Investigator.

B.6.5. Randomization

Subsequent to completing Baseline assessments, qualifying subjects will be randomly assigned to either one of the two study treatment groups: SGX-SCS programming or Standard SCS programming (active comparator). Randomization will be stratified by gender and whether the subject has bilateral or unilateral leg pain at Baseline. Randomization will be done at each study site by randomly permuted blocks.

B.6.6. SCS Trial Phase

Subjects will undergo a Trial Phase with the randomly assigned treatment group. The Trial Phase will last up to 10 days. Percutaneous leads will be placed in the epidural space at a

vertebral level based on the subject's pain condition and pain pattern as described in the Physician Implant Manual. Stimulation will be delivered from an external neurostimulator (ENS).

Anterior-posterior (AP) and lateral X-ray imaging will be done following lead implantation at the beginning of the Trial Phase and when significant lead migration is suspected.

Stimulation therapy will be as follows for each study arm:

- For Standard SCS: stimulation parameters will be trialed according to standard practice as described in the Intellis™ labeling/manuals.

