Stimgenics reserves the right to stop the enrollment of subjects at any clinical site at any time after the clinical site initiation. Possible reasons for suspending or terminating a clinical site may include, but are not limited to:

- Non-compliance by Investigator
- Failure to obtain proper written informed consent
- Repeated failure to complete or submit eCRFs in a timely manner
- Failure to report SAEs to the Sponsor within 48 hours of knowledge of the event and to reviewing IRB in accordance with its policies
- Repeated failure to comply with clearance of queries generated during monitoring of the study
- Inactivity

B.7. Study Endpoints

B.7.1. Definition of Analysis Populations

- Intent to Treat (ITT): All randomized subjects.
- Modified Intent to Treat (mITT): All randomized subjects who complete the Trial Phase.

B.7.2. Effectiveness Assessment Definitions

- Primary Effectiveness Assessment: For subjects who have a successful Trial Phase and receive a permanent implant, the Primary Efficacy Assessment occurs at the follow up visit 3 months after Device Activation. For subjects who do not have a successful Trial Phase, the Primary Efficacy Assessment occurs at the end of the Trial Phase.

B.7.3. Primary Endpoint

Pain rating on the 10 cm Visual Analog Scale is considered the primary outcome measure. VAS is the most widely used outcome measure in assessing pain due to its documented reliability and validity, ease in administration, and minimal training requirements for the administrator.

- ***Individual Responder:*** A decrease in back pain VAS by at least 50% at 3 months Post-Permanent Device Activation as compared with Baseline.

Overall Study Success: The percentage of Individual Responders in the test group is shown to be statistically non-inferior to the percentage in the control group.

B.7.4. Secondary Endpoints

The following secondary endpoints will be evaluated:

- Comparison of the percentage of Individual Responders between the test and control groups in a statistical test of superiority
- Comparison of change from Baseline in back pain score (VAS) determined at the 3-month visit after device activation, between test and control in a statistical test of non-inferiority. This is calculated as: Change from Baseline in Back Pain VAS = 3-Month Visit Pain VAS – Baseline Pain VAS. A negative result reflects a decrease in the Pain VAS, while a positive result reflects an increase in Pain VAS.

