- If the primary efficacy endpoint in the test group is found to be non-inferior to that in the control group, then a secondary endpoint will evaluate whether the proportion of subjects who achieve a 50% improvement in their back pain VAS score at 3 months in the test group is superior to that in the control group. A superiority test based on the difference in proportions will be performed based on the following null hypothesis, with a one-sided p-value of 0.05 or less considered evidence of statistical significance.

H_0 : The proportion of subjects (P) who achieve a 50% improvement in their back pain VAS score at 3 months in the Test group is less than or equal to that in the Control group.

$$P_{\text{Test}} \leq P_{\text{Control}}$$

H_1 : The proportion of subjects (P) who achieve a 50% improvement in their back pain VAS score at 3 months in the Test group is greater than that in the Control group.

$$P_{\text{Test}} > P_{\text{Control}}$$

- Change in mean VAS will be evaluated with two-sample t-test of non-inferiority in means with a 0.65 cm margin at 3 months.

H_0 : The change (C) in subject's VAS pain intensity score relative to baseline at the Primary Efficacy Assessment in the Test group is inferior to that of subjects in the Control group (active control).

$$C_{\text{Test}} \geq C_{\text{Control}} - 0.65 \text{ cm}$$

H_1 : The change (C) in subject's VAS pain intensity score relative to baseline at the Primary Efficacy Assessment in the Test group is not inferior to that of subjects in the Control group (active control).

$$C_{\text{Test}} < C_{\text{Control}} - 0.65 \text{ cm}$$

The non-inferiority margin of 0.65 cm was selected based on a previous study of a similar therapy against traditional SCS.⁸ In that study, the experimental therapy showed a 4.9 point improvement while traditional SCS showed a 3.6 point improvement for a difference of 1.3 points. Taking 50% of this treatment effect yields the margin of 0.65.

The following secondary endpoints do not have an associated hypothesis, and no significance level will be assigned to statistical tests that may be performed.

- Comparison of Back Pain Treatment Success (responder rate), measured as subjects with at least a 50% reduction in Back Pain VAS, evaluated at 6-months after device activation, between test and control:
- Comparison of mean change from Baseline in Back Pain VAS, evaluated at 6-months after device activation, between test and control

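### In B.9.2.2 the hypotheses for the 3-month VAS-change test carry the wrong sign: as printed they test superiority by more than 0.65 cm, not non-inferiority

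*Combined protocol and SAP*

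**What the plan says.** The test is set out in B.9.2.2: "Change in mean VAS will be evaluated with two-sample t-test of non-inferiority in means with a 0.65 cm margin at 3 months". Beneath it the plan prints

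- H0: C_Test ≥ C_Control − 0.65 cm
- H1: C_Test < C_Control − 0.65 cm

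In words, H1 says that the change "at the Primary Efficacy Assessment in the Test group is not inferior to that of subjects in the Control group".

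B.7.4 gives the scale. Change is the 3-month VAS minus the baseline VAS, and: "A negative result reflects a decrease in the Pain VAS, while a positive result reflects an increase in Pain VAS". The same item describes the endpoint as "determined at the 3-month visit after device activation, between test and control in a statistical test of non-inferiority".

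The margin comes from a cited study in which the experimental therapy improved by 4.9 points, while "traditional SCS showed a 3.6 point improvement for a difference of 1.3 points"; half of that difference is taken.

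The assessment time is stated in more than one way. The hypotheses refer to the Primary Efficacy Assessment, and B.7.2 adds: "For subjects who do not have a successful Trial Phase, the Primary Efficacy Assessment occurs at the end of the Trial Phase". B.9.2.4 uses Trial Phase results of failed trials for the primary endpoint and sends any other data to multiple imputation.

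No covariate is named for the test. Baseline back pain is collected before randomization (B.6.3: "Assessments for eligibility include average pain intensity (which will be used as Baseline pain intensity), medication usage"), and B.6.5 states: "Randomization will be stratified by gender and whether the subject has bilateral or unilateral leg pain at Baseline".

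**The concern.** The words and the inequalities describe different tests. This is the only secondary comparison of means with a stated hypothesis and margin, so its decision rule should be unambiguous. An analyst who follows the symbols will almost always fail to conclude non-inferiority when the two programming approaches are equally good. An analyst who follows the words departs from the printed hypothesis, and in an open-label trial that departure would be hard to defend after the data are seen.

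Three further gaps sit in the same item. No alpha is given, although the primary test and the superiority secondary test each state one-sided 0.05. The visible text does not say whether the ITT or the mITT set of B.7.1 is used. It is also unclear which value a failed-trial subject contributes: the end-of-trial VAS (B.7.2 and the hypotheses), an imputed 3-month VAS (B.9.2.4 read literally), or neither (B.7.4 read literally).

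**Working it through.** **The plan's own figure.** 4.9 − 3.6 = 1.3, and 0.5 × 1.3 = 0.65 cm. The size of the margin reproduces; only its sign in the hypotheses is at issue.

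**Sign.** Let D = C_Test − C_Control, with negative change meaning improvement. Test is worse by the margin when D = +0.65, so non-inferiority is H1: D < +0.65. The plan prints H1: D < −0.65, which is superiority by more than 0.65 cm. Reversing the scale so that positive means improvement does not help: the printed H1 would then say that Test is worse by more than 0.65 cm. Neither convention makes symbols and words agree. The two boundaries lie 0.65 − (−0.65) = 1.3 cm apart.

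**Inputs for the size of the effect.** From the plan: 50 per arm (B.5.5.1). Assumed, because the documents give no SD, correlation or alpha for this test: follow-up SD 2.5 cm, baseline SD 1.0, 1.25 or 1.5 cm, correlation r from 0.1 to 0.5 in steps of 0.1, one-sided alpha 0.05. The change SD is √(s0² + s1² − 2·r·s0·s1):

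- smallest: √(1.5625 + 6.25 − 3.125) = 2.17 cm (s0 = 1.25, r = 0.5)
- largest: √(2.25 + 6.25 − 0.75) = 2.78 cm (s0 = 1.5, r = 0.1)

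**What each rule demands of the data.** SE = SD × √(2/50) = 0.2 × SD, and the critical t on 98 df is 1.661. At SD 2.5, SE = 0.50. As printed, the observed D must be below −0.65 − 1.661 × 0.50 = −1.48 cm. As intended, it must be below +0.65 − 0.83 = −0.18 cm.

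**Chance of passing** (noncentral t, change SD about 2.2 to 2.8 cm):

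| True advantage of Test | As printed | As intended |
|---|---|---|
| 0 cm | 0.1–0.3% | 31–44% |
| 0.5 cm | 2.3–2.8% | 66–84% |
| 1.3 cm (the cited study's difference) | 31–44% | 97–99.8% |

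A wider SD range of 2.0 to 3.0 cm gives the same picture at no true difference: 0.1–0.3% against 28.5–48.8%.

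**Would covariate adjustment matter?** ANCOVA against the t-test on change has variance ratio s1²(1 − r²)/(s0² + s1² − 2·r·s0·s1). Multiplying by 1 + 3/(N − 6) charges for three covariates; at N = 100 this is 1 + 3/94 = 1.032. The strata are assumed not prognostic.

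- midpoint (s0 = 1.25, r = 0.3): 5.6875/5.9375 = 0.958; × 1.032 = 0.988, about 1% less variance
- best (s0 = 1.5, r = 0.1): 6.1875/7.75 = 0.798; × 1.032 = 0.824, about 18% less
- worst (e.g. s0 = 1.25, r = 0.5): 1.000 × 1.032 = 1.032, about 3% more

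Six of the 15 combinations are small net losses. With the corrected boundary and a true 0.5 cm advantage, power changes by −1.1 to +7.3 points; at the midpoint it goes from 75.8% to 76.2%.

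**The case against.** The strongest reply is that nobody would be misled. The label non-inferiority, or its equivalent, stands in B.7.4, in the sentence naming the test, in the words of both hypotheses and in the margin rationale. An analyst would probably use +0.65 cm, and the percentages for the printed rule describe a literal reading under assumed SDs and an assumed alpha. This is fair as to likelihood. It does not remove the contradiction: the whole item is readable, no redaction falls inside it, and a prespecified rule should not depend on the analyst overriding its formula.

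A reader might also infer that the unadjusted t-test is itself a flaw, because baseline VAS and the strata are available. The documents do not support that. The t-test is valid, with no bias or type I error problem; a change score already uses the baseline; and entry at 5.0 cm or more on a 10 cm scale limits the baseline spread. The gain from adjustment could be slightly negative. A one-standard-error chance imbalance in baseline VAS at 50 per arm would shift the change-score difference by −0.05 to +0.25 cm, and by 0.10 cm at the midpoint against a standard error of about 0.49 cm. Redacted text around B.9.2.3 and at the end of B.9.2.4 may already hold an adjusted model.

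**Conclusion.** The sign error is established from the documents alone and should be corrected before analysis. It moves the boundary by 1.3 cm and changes the question from non-inferiority to superiority by a margin. The percentages depend on the assumed SDs, correlations and alpha; the contradiction does not. The missing alpha, the unnamed population and the conflicting time point are gaps to close in the same edit.

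Two stronger conclusions should not be drawn. First, the error does not touch study success: B.8.2 rests success on the primary responder test alone and sets no success criterion for secondary endpoints, and the primary hypotheses in B.9.2.1 carry the correct sign. Second, ANCOVA is not required. It is a reasonable low-cost option whose precision benefit the documents cannot settle, and it gives no ground for a smaller sample.

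**What to change.** In B.9.2.2:

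1. Restate H0: C_Test − C_Control ≥ +0.65 cm and H1: C_Test − C_Control < +0.65 cm. Non-inferiority is shown when the upper one-sided 95% confidence limit of Test minus Control is below +0.65 cm.
2. State one-sided alpha 0.05 for this test, matching the primary and the superiority secondary test.
3. Name the analysis population (ITT or mITT, B.7.1).
4. Choose one rule for failed trials, give the reason, and align B.7.4, B.9.2.2 and B.9.2.4 with it. Using the end-of-trial value mixes readings taken within 10 days of stimulation with 3-month readings. Imputing a 3-month value for subjects who never received the implant answers a different question. The choice should be explicit.

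Optional: prespecify an ANCOVA of VAS change on treatment, baseline VAS, gender and leg-pain laterality as the main estimator, with the same covariates in the imputation model and the t-test as supportive, unless redacted text already does so. Do not reduce the sample size on account of it.

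Cost: items 1 to 4 are wording only. The ANCOVA needs a few lines of code and no new data; its worst case over the assumed range is about 1 point of power.

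### The 3-month VAS-change hypotheses carry the 0.65 cm margin with the wrong sign, so the test labelled non-inferiority demands superiority by more than 0.65 cm

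*Combined protocol and SAP*

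**What the plan says.** Section B.7.4 lists, among the secondary endpoints, the 3-month change in back pain VAS, to be compared "between test and control in a statistical test of non-inferiority". It defines the variable as "Change from Baseline in Back Pain VAS = 3-Month Visit Pain VAS – Baseline Pain VAS" and states the direction: "A negative result reflects a decrease in the Pain VAS, while a positive result reflects an increase in Pain VAS".

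Section B.9.2.2 names the method: "Change in mean VAS will be evaluated with two-sample t-test of non-inferiority in means with a 0.65 cm margin at 3 months". In words, its null hypothesis is that the test arm is inferior to control and its alternative is that it is not. In symbols, the null is "C_{\text{Test}} \geq C_{\text{Control}} - 0.65 \text{ cm" and the alternative is "C_{\text{Test}} < C_{\text{Control}} - 0.65 \text{ cm".

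The same section derives the margin from a cited study in which "the experimental therapy showed a 4.9 point improvement while traditional SCS showed a 3.6 point improvement for a difference of 1.3 points". It continues: "Taking 50% of this treatment effect yields the margin of 0.65".

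**The concern.** When lower values are better, a non-inferiority margin is an allowance added to the control mean: the test arm may be worse by up to that amount. Here it is subtracted. The printed alternative then asks the test arm to beat control by more than the margin, although the sentence above it claims only that the test arm is not inferior.

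The words and the formula therefore specify two different tests. An analyst who codes the formula runs a test of superiority by a margin, and a therapy that meets the stated aim will usually fail to show non-inferiority. An analyst who follows the words departs from the printed hypotheses. The study is open-label and has no data monitoring committee, so choosing between the two once results are known would look post hoc. This is also the only test with a formal hypothesis on mean pain change. The one other secondary endpoint with a hypothesis is responder superiority.

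**Working it through.** **The margin.** 0.5 × (4.9 − 3.6) = 0.5 × 1.3 = 0.65 cm. This reproduces the plan's figure, so the size of the margin is not in question here, only its sign.

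**The sign.** Let C be the 3-month score minus baseline (B.7.4), so that lower is better. Let d = C_Test − C_Control.

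- Non-inferiority with margin 0.65: H0 is d ≥ +0.65 and H1 is d < +0.65.
- As printed in B.9.2.2: H0 is d ≥ −0.65 and H1 is d < −0.65.

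As an example, take a control change of −3.6, the improvement quoted for traditional SCS. The printed H1 needs a test change below −3.6 − 0.65 = −4.25. Non-inferiority needs one below −3.6 + 0.65 = −2.95. Every test change from −4.25 up to −2.95, including exact equality at −3.6, is non-inferior by the stated margin (the −2.95 endpoint excluded) but lies in the printed null.

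**The opposite convention.** If C meant improvement, with higher better, non-inferiority would be C_Test > C_Control − 0.65. The printed H1 uses <, so it would say that the test arm is worse by more than 0.65 cm. The formula contradicts its label under either convention, and B.7.4 fixes which one applies.

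**Size of the effect.** Inputs:

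- n = 50 per arm, the minimum in B.5.5.1.
- One-sided alpha of 0.05. This is assumed: the plan gives it for the primary test and the responder superiority test, but not for this one.
- SD of change of 2.0, 2.5 or 3.0 cm. These are assumed, because the documents give none.

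Using a normal approximation, SE = SD × √(2/50), which is 0.40, 0.50 and 0.60 cm.

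- Corrected sign: P(reject H0) = Φ((0.65 − d)/SE − 1.645)
- As printed: P(reject H0) = Φ((−0.65 − d)/SE − 1.645)

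For SD 2.0 and d = 0, the corrected test gives Φ(1.625 − 1.645) = Φ(−0.02) = 49.2%. The printed test gives Φ(−1.625 − 1.645) = Φ(−3.27) = 0.05%.

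| True d (cm) | Test | SD 2.0 | SD 2.5 | SD 3.0 |
|---|---|---|---|---|
| 0 | corrected | 49.2% | 36.5% | 28.7% |
| 0 | as printed | 0.05% | 0.16% | 0.32% |
| −0.65 | corrected | 94.6% | 83.0% | 69.9% |
| −0.65 | as printed | 5.0% | 5.0% | 5.0% |
| −1.3 | corrected | 99.9% | 98.8% | 94.6% |
| −1.3 | as printed | 49.2% | 36.5% | 28.7% |

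**The hurdle in observed terms.** The printed test rejects when the observed d is below −0.65 − 1.645 × SE, that is, below −1.31, −1.47 or −1.64 cm. The corrected test rejects when it is below 0.65 − 1.645 × SE, that is, below −0.01, −0.17 or −0.34 cm. The two thresholds differ by 1.3 cm, twice the margin, whatever the SD or alpha.

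**The case against.** The strongest reply concerns weight. Section B.8.2 ties study success to the primary non-inferiority test alone and sets no success criteria for secondary endpoints. The responder superiority test depends only on the primary result, and the sample size rests on the responder rates. The error also works against the sponsor: it makes success harder and cannot produce a false claim of non-inferiority. All of this stands, and it limits the consequences to one secondary result.

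A second reply is that the intent can be recovered. B.7.4, the method statement, the verbal hypotheses and the derivation of the margin all say non-inferiority, and only the two symbolic lines disagree. That is a fair account of what was meant, and it supports the proposed correction. It does not make the printed decision rule usable.

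Third, the sign does not explain every failure. Even with the correct sign, two truly equal arms would fail in 51% to 71% of trials under the assumed SDs, because 50 per arm is small for a 0.65 cm margin. Failing to reject H0 also does not establish inferiority. Both points are right, and the comparison above is of the two versions of the test on the same data.

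A fault in reading the PDF is unlikely, since the minus sign appears in both lines. The sponsor can settle that against the source file.

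**Conclusion.** The point holds. The formula in B.9.2.2 contradicts the plan's own definition of change and its own statement of what is being tested, and nothing elsewhere in the documents corrects it. As printed, this is a test of superiority by more than 0.65 cm.

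The direction of the error, and the 1.3 cm gap between the two rejection thresholds, depend on no assumption. The probabilities rest on the normal approximation, 50 per arm, and the assumed alpha and SDs. A likely origin is the primary hypotheses in B.9.2.1, where higher is better and the margin is correctly subtracted. The inequality seems to have been turned round for VAS without turning the sign of the margin, but that is inference.

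The endpoint is secondary, yet the fault lies in the decision threshold of a prespecified test, so it should be corrected before that test is run.

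**What to change.** In B.9.2.2, change both symbolic lines:

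- H0: C_Test ≥ C_Control + 0.65 cm
- H1: C_Test < C_Control + 0.65 cm

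Equivalently, conclude non-inferiority if the upper one-sided confidence limit for C_Test − C_Control lies below +0.65 cm. State the alpha for this test, and hence the confidence level of that limit, in the same edit. It would help to repeat beside the hypotheses that C is the 3-month score minus baseline.

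The cost is two sign changes and one added sentence, made as a documented amendment before outcome data are analysed. It needs no extra subjects or data and changes nothing in the primary analysis or the sample size.

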The implantation of a spinal cord stimulation system involves risks that are similar to other spinal procedures. In addition to those normally associated with surgery, implantation or use of a neurostimulation system includes, but is not limited to, the following risks:

- Allergic or immune system response to the implanted materials
- Infection
- Lead or neurostimulator erosion through the skin or migration
- Leakage of cerebrospinal fluid
- Loss of pain relief may return patients to their underlying pain condition
- Persistent pain at the neurostimulator site
- Placement of the epidural lead is a surgical procedure that may expose patients to risks of epidural hemorrhage (bleeding), hematoma, or paralysis
- Radicular chest wall stimulation
- Seroma (fluid collection in pocket where stimulator is placed) or hematoma at the neurostimulator site
- Change in stimulation, possibly related to cellular changes around the electrode(s), shifts in electrode position, loose electrical connections, lead fractures, which has been described by some patients as uncomfortable stimulation (jolting or shocking sensation)
- Over time there could be changes in the level of symptom control. In most cases, the physician can correct these changes without surgery.
- Formation of excessive tissue around the lead in the epidural space can result in delayed spinal cord compression and paralysis, requiring surgical intervention. Time to onset can range from weeks to many years after implant.
- The safety of this therapy is unknown for pregnancy, unborn fetus, or delivery
- Stimulation-dependent gastrointestinal symptoms such as diarrhea, incontinence or constipation
- Stimulation-dependent bladder symptoms such as urinary retention, incontinence or frequency
- Unexpected changes in stimulation - Electromagnetic interference, changes in posture, and other activities can cause a perceived increase in stimulation

System Revision Risk

The Intellis AdaptiveStim Neurostimulator may require replacement in 9 years or earlier, regardless of the number of times the neurostimulator is recharged. It is possible that the system will need to be revised (explanted, replaced, or repositioned) earlier than 9 years. Possible reasons for revision/explant may include infection, malfunction, and migration of the system components. The risks associated with system revision are equivalent to the commercially available systems.

Pregnancy Risks

Pregnant women are not able to take part in this study. Female subjects must agree to not become pregnant during the study by using a medically acceptable method of birth control. If a subject becomes pregnant during this study, there may be risks to the unborn child that are not yet known. Subjects will be advised and encouraged to notify the study doctor immediately if they think they are or have become pregnant. Subjects that become pregnant during the study will be instructed to turn the neurostimulator “OFF” and will be exited from the study.

Radiographic Imaging

As part of the study, subjects may be required to have fluoroscopic or X-ray images taken of their thoracic spine in addition to the imaging conducted to implant the leads. This may be beyond what is standard of care. The risk associated with these additional images has been considered and determined to be minimal since the total radiation dose will be approximately the same as one CT scan of the abdomen.

Study Risk Control Measures

The following will be done to mitigate risks associated with the implanted system:

- Investigators who are experienced with spinal cord stimulation implantation techniques will be utilized
- Instructions will be given to the study participants to ensure they can properly use the patient programmer and recharger system
- Subjects can turn off stimulation at any time during the study with the patient programmer or recharger
- Periodic monitoring of the study participants
- Written materials that contain precautions, warnings, and contraindications, as well as instructions on the use of the devices will be available and/or provided to the clinicians and subjects

Since the efficacy measure in this study is intensity of pain in the back and legs, pain in these areas does not need to be reported as an adverse event unless it meets the definition of a serious adverse event. However, Investigators may, at their discretion, report any other pain-related adverse events during the study.

C2. Minimization of Risks

The study will use commercially available Intellis™ SCS system within the approved indications for use. The risks associated with the use of SCS systems have been well characterized and are minimal compared to the side effects associated with most surgical procedures or the use of many medications used to treat chronic pain conditions. Additionally, SCS therapy is reversible since the SCS device may be turned off and the SCS system may be explanted at any time for any reason.

Study Investigators are experienced in the diagnosis and treatment of chronic pain, have proper surgical and clinical training and will take adequate steps to ensure subject safety throughout the entire study.

Investigators and study personnel will receive product training to become familiar with the components of the Intellis™ SCS systems and their functions. They will also receive training on assessment tools and Good Clinical Practice (GCP) in the conduct of clinical trials with human participants.

D. Description of the Device

D.1. Each Important Component, Ingredient, and Property of the Device

D.1.1. Device System Overview

The Intellis™ system is a totally implantable spinal cord stimulation system that is indicated to aid in the management of chronic intractable pain of the trunk and/or limbs. The system has been approved by the FDA and is available for commercial use.

The Intellis system system consists of a rechargeable implantable neurostimulator (INS) with 16 output channels. The INS is implanted in a subcutaneous pocket and is capable of stimulating the dorsal aspect of the spinal cord when used with one or two 8-contact percutaneous leads located in the epidural space. The INS can be controlled by a Patient Programmer and/or a Clinician Programmer.

Before permanent implantation, a trial phase of therapy lasting up to 10 days is required. Components of the system during trial include an External Neurostimulator (ENS) capable of delivering the same stimulation as the INS, and Stimulation Leads. Other components of the system include Clinician Programmer, Communicator, Patient Programmer, Extensions, Charger and charging system, and surgical accessories.

D.1.2. Device System Details

Only FDA approved, commercially available components will be used for the study.

D.1.2.1 Major Components

Implantable Neurostimulator: Intellis neurostimulator (Model 97715, Medtronic, Minneapolis MN) will be used for the study. The INS is a multi-programmable, rechargeable device that delivers stimulation through one or two 8-electrode leads. The stimulation settings are stored in programs. A program is a specific combination of pulse width, rate, and amplitude settings acting on a specific electrode combination (up to 16 electrodes per program). Each of the 16 electrodes in the leads can be set to be a

cathode, an anode, or to remain off. The INS is powered by a Li-Ion rechargeable battery. The INS is capable of stimulating the dorsal aspect of the spinal cord through the electrodes in the leads that are connected to the output terminals of the INS. The electrical pulses used for stimulation are generated using a single current source. The INS is designed to produce charge-balanced, biphasic rectangular pulses.

The battery is recharged using an external charger that uses transcutaneous RF energy transmission. The INS is capable of communicating with the Charger to control the recharging function.

The INS communicates with the Clinician Programmer and Patient Programmer (also called Patient Remote Controller). Clinician Programmer is used to program the INS and the ENS. The Patient Programmer is used by the subject to control some of the therapy parameters, change therapy programs, and turn stimulation on and off.

External Neurostimulator (ENS) for Trial Phase: The Medtronic Model 97725 Wireless External Neurostimulator (ENS) is part of a neurostimulation system used for trial stimulation outside of the operating room. The ENS is powered by two standard alkaline AAA batteries. The ENS is connected to leads implanted in the subject. The subject uses the ENS during the Trial Phase to evaluate the effectiveness of SCS therapy prior to receiving a permanent implant. The ENS also communicates with the Clinician Programmer system and Patient Remote Controller, similar to the INS.

Clinician Programmer System: The Medtronic Model A710 Intellis™ clinician programmer application resides on a tablet and is intended to be used by healthcare professionals to program the ENS (Model 97725) and Intellis™ INS (Model 97715 and 97716) for pain therapy. The Clinician Programmer requires the use of the Communicator (Model 8880T2) to communicate with the INS.

Patient Programmer: The Patient Programmer (Model 97745), also called Patient Remote Controller, is a handheld unit able to communicate with the INS or ENS. The Patient Programmer is powered by two standard AA alkaline batteries. The Patient Programmer is used by subjects to select the SCS therapy program to be applied, to turn on or off the INS or ENS, and to change some of therapy parameters such as stimulation amplitude.

Charging System: The Charging system (Model 97755) is used by the subject to transcutaneously charge the INS battery. It is a portable device powered by a rechargeable battery and can be held in one hand. The charging system used in this study is a commercially available charging system manufactured by Medtronic (Minneapolis, MN) and fully compatible with the study INS.

Stimulation Leads and Lead Extensions: The study will use commercially available percutaneous eight-electrode leads manufactured by Medtronic (Minneapolis, MN) and compatible with the INS and ENS to be used in this study. The leads are positioned percutaneously in the epidural space of the subject and are used for delivering the stimulation field to the dorsal aspect of the spinal cord. The percutaneous leads are intended to be single use. Temporary or permanent percutaneous leads may be used during the Trial Phase of the study. The proximal end of these leads connect directly to the ENS. Permanent leads will be used during the Permanent Phase of the study. These

may be connected to a Lead Extension. The leads or lead extensions are tunneled subcutaneously to connect to the INS. Commercially available lead extensions (Medtronic, Minneapolis, MN) compatible with the percutaneous leads and INS may be used in this study.

D.1.2.2. Surgical Accessories

The surgical accessories that will be used in the study will be commercially available devices.

Torque Wrench: A commercially available Torque Wrench is used to tighten the screws that lock a percutaneous lead into the INS and/or a lead extension. It also tightens the screws that lock the lead extension into the INS when this is used.

Lead anchors: Lead anchors may be used to possibly prevent lead migration and/or lead strain. These are used to anchor the percutaneous leads to the supraspinous ligament or fascia. Lead anchors used in this study are commercially available (Medtronic, Minneapolis, MN) and designed to slide freely over the lead length to the required fixation position. Surgical sutures are then tied around the anchor clamping the sleeve in place on the lead.

Insertion Needle: Percutaneous leads are implanted in the dorsal epidural space using insertion needles. An insertion needle contains a cannula and stylet that facilitate access to the spinal canal for lead placement. The insertion needle is a 14G epidural needle with a thin wall and a modified Touhy non-coring tip. The cannula and stylet are designed to lock together and maintain the orientation of the tip of each component. The hub of the insertion needle has a standard luer fitting.

Stylets: Stylets are used to push and “steer” a percutaneous lead into the desired place within the epidural space. The distal end of the stylet could be straight or curved. The implanter is able to use either one in order to comfortably maneuver a percutaneous lead through the epidural space until it reaches the desired implant location.

Tunneling Tool: A Tunneling Tool is used to create a subcutaneous tunnel that directs the percutaneous leads or lead extensions from the midline incision to the leads from the INS implant site. This is a single use tool.

INS Template: The INS Template is an aid to be used for the implanter intended for proper sizing of the INS pocket within each subject.

INS Port Plug: An INS Port Plug is used to seal the port of the INS that is not in use when only one percutaneous lead is implanted.

Lead Blank: A Lead Blank is an optional aid made out of flexible stainless steel that has an outer diameter similar in size to the percutaneous lead. A lead blank can be optionally used to clear a path for the introduction of a percutaneous lead into the epidural space.

D.2. Principle of Operation of the Device

Only commercially approved Intellis™ SCS system will be used according to its indications for use. Spinal cord stimulation therapy for pain management has been used for more than four decades. Its efficacy and safety has been widely documented.

D.3. Labeling

Instructions for Use: The study devices will be used in accordance with Intellis™ Manual.

D.4. Any Anticipated Changes in the Device

There are no anticipated changes at this time.

E. Administrative Procedures

[REDACTED]

[REDACTED]

[REDACTED]

[REDACTED]

[REDACTED]

[REDACTED]

[REDACTED]

E.3. Study Conduct

The Investigator agrees that the study will be conducted according to this investigation plan, the principles of GCPs as outlined in the United States Code of Federal Regulations (CFR) - 21 CFR Parts 50, 56 and 812, and the Sponsor internal standard operating procedures. The

Investigator will conduct all aspects of the study in accordance with all Federal and local laws of pertinent regulatory authorities.

The Investigator will assure correct implementation and conduct of the trial including those study related duties delegated to other appropriately qualified individuals and designated in the delegation of authority documentation. The Investigator will assure that study staff cooperates with monitoring and audits, and will demonstrate due diligence in recruiting, screening, and retaining study subjects.

The Investigator will also be responsible for filing an annual study progress report to the IRB as per IRB guidelines. The Investigator and/or Sponsor, as required by local regulations, are required to report in writing to the IRB, notice of completion, termination, or discontinuation of the study. If the study is discontinued for safety concerns, the Investigator and/or Sponsor will notify the IRB immediately.

The Investigator is also responsible for recording and assessing the severity of Adverse Events. Investigators must report any severe adverse event (SAE) to the sponsor within 48 hours of knowledge of the event and to the IRB as per their regulations.

The Investigator is also responsible for promptly reporting to the Sponsor any deviations and exceptions to this investigational plan and to the IRB per their requirements.

E.4. Informed Consent Materials

Informed consent must be obtained from all subjects prior to study participation. Informed consent will be obtained by the Investigator or an Investigator-designated healthcare professional as per GCP guidelines. An informed consent form (ICF) will be provided to potential subjects for their private evaluation. If a subject consents to participate, the ICF must be signed by the subject or a legally authorized representative of the subject. Study ICF must be approved by the IRB. Signed ICFs will be retained in the subject's study records at the clinical site.

